## **6.2 Other treatment(s)**

### **6.2.1 Concomitant therapy**

In general, the use of any concomitant medication/therapy deemed necessary for the care of the participant (e.g., such as anti-emetics, anti-diarrheal) is permitted, except when specifically

prohibited (see [Section 6.2.2](#)). The participant must be told to notify the investigational site about any new medications he/she takes after the start of the study drug.

Participants should not receive pre-medication to prevent infusion reaction before the first infusion of MBG453 (sabatolimab). If a participant experiences an infusion reaction, he/she may receive pre- medication on subsequent dosing days. The pre-medication should be chosen per institutional standard of care, at the discretion of the treating physician. If a participant experiences a Grade 3 or Grade 4 infusion reaction, the investigational drug should be discontinued.

Acute allergic reactions should be treated as needed per institutional standard of care. In the event of anaphylactic/anaphylactoid reactions, this includes any therapy necessary to restore normal cardiopulmonary status. If a participant experiences a Grade 3 or Grade 4 anaphylactic/anaphylactoid reaction, the investigational drug should be discontinued.

MBG453 (sabatolimab) should be administered in a facility equipped for cardiopulmonary resuscitation. Appropriate resuscitation equipment should be available and a physician should be readily available.

Participants should receive appropriate prophylaxis (e.g., antiemetics) for HMA as per local practice.

Relevant prior and all concomitant medication and non-drug therapies will be collected. Blood transfusions taken within 16 weeks before enrollment and during the course of the study should be recorded in the appropriate case report form (CRF). Transfusion should be collected every 2 months during post-treatment follow-up.

Each concomitant drug must be individually assessed against all exclusion criteria/prohibited medication. If in doubt, the investigator should contact the Novartis medical monitor before enrolling a participant or allowing a new medication to be started. If the participant is already enrolled, contact Novartis medical monitor to determine if the participant should continue study treatment.

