#### **12.5.1.8 Improvement in RBC/platelets transfusion independence**

Number and percent of patients who are RBC/platelets transfusion independent after the date of the first dose of study medication as per IWG-MDS.

RBC/Platelets transfusion independence rate is defined as the proportion of participants having received <0 units RBC/Platelets transfusions during at least 8 consecutive weeks after enrollment ([Table 8-2](#)). The number and percentage of patients will be shown for the overall FAS and then also in only those with transfusion dependence at baseline. Percentages will be provided with exact 95% Clopper-Pearson confidence intervals.

For participants with at least one period of transfusion independence post-baseline, the total duration of all transfusion independence periods (which all individually must be at least 8 weeks) will be also summarized.

The duration of each period of transfusion independence is defined from the end date of the last transfusion received until the date transfusions are given again or last date of treatment administration in case transfusions had not (re-)started during treatment. The total duration of all transfusion independence periods is the sum of each period of the transfusion independence.

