2.7.1.7 Time to Complete Remission

Time to Complete Remission is defined as the time from the date of enrollment (cycle 1 day 1) to the first documented CR.

Time to complete remission will be analyzed using the Kaplan-Meier Product-Limit method. Subjects who are known to be without CR will be censored at study-maximum follow-up time (i.e. Last Subject Last Visit (LPLV) for final analysis, for analysis of cut-off date min (LPLV, Cut-off date)) for subjects with a PFS event (i.e. disease progression or death due to any cause), or at the date of the last adequate assessment for subjects without a PFS event. Estimates of the 25th, median and 75th percentile of the time to CR and their 95% confidence intervals Kaplan-Meier plots will be provided, if applicable. Improvement in RBC/platelets transfusion independence

The number and percent of subjects who are RBC/platelets transfusion independent after the date of enrollment as per IWG-MDS will be provided.

RBC/Platelets transfusion independence rate is defined as the proportion of subjects having received <0 units (no RBC/Platelets transfusions) during at least 8 consecutive weeks after enrollment ([Table 2-6](#)). The number and percentage of subjects will be shown for the overall FAS and then also in only those with transfusion dependence at baseline. Percentages will be provided with exact 95% Clopper-Pearson confidence intervals. Bar graphs will be provided.

For subjects with at least one period of transfusion independence post-baseline, the total duration of all transfusion independence periods (which all individually must be at least 8 weeks) will be also summarized.

The duration of each period of transfusion independence is defined from the end date of the last transfusion received until the date transfusions are given again or last date of treatment administration in case transfusions had not (re-)started during treatment. The total duration of all transfusion independence periods is the sum of each period of the transfusion independence.

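### The start rule for transfusion-independence duration has no lower bound at enrolment, so it can count pre-enrolment time, and it gives never-transfused participants no start date

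*SAP*

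**What the plan says.** The duration rule is in SAP 2.7.1.7, in the text on transfusion independence that runs on from time to complete remission. The duration of each period "is defined from the end date of the last transfusion received until the date transfusions are given again". For a participant with no further transfusion on treatment, the SAP closes the period at the final dose: "or last date of treatment administration in case transfusions had not (re-)started during treatment". Protocol 12.5.1.8 has the same start rule: "The duration of each period of transfusion independence is defined from the end date of the last transfusion received".

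The summary is planned as follows: "For subjects with at least one period of transfusion independence post-baseline, the total duration of all transfusion independence periods", with the condition "which all individually must be at least 8 weeks". The rate reported beside it requires no transfusion "during at least 8 consecutive weeks after enrollment", and its counts and percentages "will be shown for the overall FAS and then also in only those with transfusion dependence at baseline".

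Other relevant text:

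- Protocol 6.2.1 sets the look-back: "Blood transfusions taken within 16 weeks before enrollment and during the course of the study should be recorded". Protocol 8.2 repeats the 16 weeks among the baseline data, and SAP 2.4.2 lists transfusions both before and after the start of treatment.
- SAP Table 2-6 defines independence after baseline as zero units in an 8-week window on study, which needs no earlier transfusion. It defines dependence at baseline as 3 or more units in the preceding 8 weeks.
- SAP 2.7.3 rules out imputation for efficacy endpoints. SAP 5.9 points to a programming macro that is not reproduced.

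**The concern.** The start date is tied to a transfusion and not to study entry. Pre-enrolment transfusions are in the database, so for someone last transfused before enrolment the only date that fits the rule lies before the study began. Weeks before treatment would then be reported as transfusion-free time under treatment. A participant with no recorded transfusion has no date that fits the rule, yet meets the on-study definition of independence and counts in the rate.

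At stake is agreement between two figures that will be read side by side for the eighth secondary endpoint: the rate, which is limited to time after enrolment, and the duration, which is not. With 39 participants, a few such cases can move a summary statistic.

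**Working it through.** The documents give no figure for duration, so there is none to reproduce. The check is date arithmetic.

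Inputs:

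- Enrolment is day 0.
- *g* is the number of days from the end of the last pre-enrolment transfusion to enrolment. The 16-week look-back gives 0 ≤ *g* ≤ 16 × 7 = 112 days.
- For participants dependent at baseline, at least 3 units fall in the preceding 8 weeks. Taking baseline as the enrolment date, *g* is at most about 8 × 7 = 56 days.
- *T* is the day the first period ends: the next transfusion or, failing that, the last treatment administration. The documents give no distribution for *g* or *T*, so the values below are assumptions.

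Formulas:

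- Duration as written = *T* + *g*
- Duration with the start bounded at enrolment = *T*
- Relative excess = *g* / *T*

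Results (days as written, with excess over *T*):

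| *T* (days) | *g* = 28 | *g* = 56 | *g* = 112 |
|---|---|---|---|
| 56 | 84 (+50.0%) | 112 (+100.0%) | 168 (+200.0%) |
| 168 | 196 (+16.7%) | 224 (+33.3%) | 280 (+66.7%) |
| 344 | 372 (+8.1%) | 400 (+16.3%) | 456 (+32.6%) |

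In months of 30.4375 days (SAP 2.1.1.5), the case *T* = 168, *g* = 28 is 196/30.4375 = 6.44 against 168/30.4375 = 5.52. The absolute excess never exceeds 112/30.4375 = 3.68 months from recorded data.

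The excess enters once, in the first period. Periods that follow an on-study transfusion are the same under both rules, so the relative excess in a participant's total is smaller when there are later periods that also count.

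The 8-week minimum can be affected in one situation. Suppose a first period has 42 on-study days after a 14-day gap. As written it lasts 42 + 14 = 56 days and meets the minimum, although only 42 days follow enrolment. If the same participant later has a qualifying period of 84 days (assumed), the total as written is 56 + 84 = 140 days, against 84 days when the minimum is applied to post-enrolment time.

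For a participant never transfused, *g* does not exist and the duration as written is undefined. With the bounded rule it is *T*.

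**The case against.** The best defence is that the surrounding text already points to post-enrolment time. The summary is limited to participants with a post-baseline period, Table 2-6 defines that status over weeks on study, and the rate is counted after enrolment. A programmer could reasonably bound the start at enrolment without being told. The analysis is also descriptive, with no comparator and no test, and the change would come after database lock.

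Part of this stands. The consequence is limited, and the programmed rule may already be right. But the word post-baseline selects who enters the summary. A separate sentence sets the start date, and that sentence carries no such limit. Elsewhere the SAP states the limit when it wants one: time to complete remission runs from enrolment, and 2.7.3 restricts complete remission and PFS to post-enrolment assessments.

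The defence also rules out some stronger readings:

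- A reader might infer that short on-study periods let unqualified participants into the summary. They do not: entry needs a post-baseline period as Table 2-6 defines it. Only extra periods in participants who already qualify are affected.
- A reader might infer that never-transfused participants are dropped and the longest durations lost with them. No text excludes them, and nothing shows that theirs are the longest. What is missing is their start date.

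**Conclusion.** The start rule should be corrected. Followed as written, it lengthens the first period of any participant last transfused before enrolment by 0 to 112 days, or by at most about 56 days in those dependent at baseline. It also leaves never-transfused participants without a defined duration. The percentages rest on assumed gaps and period lengths; the limits in days follow from the 16-week look-back and the baseline-dependence definition.

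A reader might conclude that the trial's durations are wrong, or inflated two- or threefold. The documents do not support that. They report no durations, and the programming is not shown. A doubling or tripling needs the shortest qualifying on-study period combined with a long gap, and the 16-week gap cannot occur in participants dependent at baseline.

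The transfusion-independence rate, its confidence interval, periods that begin after an on-study transfusion and the primary safety endpoint are unaffected.

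**What to change.** In the duration text of SAP 2.7.1.7, state that:

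- a period starts at the later of the enrolment date and the end date of the last transfusion;
- it starts at enrolment when there is no earlier transfusion;
- the 8-week minimum applies to post-enrolment time, so that the duration matches the rate.

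Use one anchor throughout. Protocol 12.5.1.8 counts independence from first dose in one sentence and from enrolment in the next, while the SAP uses enrolment.

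The cost is a short insertion and one derivation change. Because the protocol has the same start rule and the latest SAP addendum was itself made after database lock, list the change in SAP section 4 as a documented post-lock clarification with its reason. If the program already bounds the start at enrolment, only the text needs to change.

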****Definition of transfusion dependence and independence for red blood cells (RBC) and/or platelets are described below.**

****maximum remission/response levels correspond to the best values reported in post baseline.*

Transfusions Status Definitions for RBC/platelets

Transfusions for intercurrent diseases not due to MDS (e.g. bleeding, surgical procedure, hemolysis, infections) should not be taken into account for the following:

Transfusion dependence:

1. At baseline: subjects having received ≥ 3 units of transfusion within the 8 consecutive weeks prior to baseline.
2. Post-baseline: subjects having received ≥ 3 units of transfusion within any 8 consecutive weeks during the course of the study.

Transfusion independence:

1. At baseline: subjects having received 0 units of transfusion within any 8 consecutive weeks prior to baseline.
2. Post-baseline: subjects having received 0 units of transfusion within any 8 consecutive weeks during the course of the study.

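### The transfusion-independence rate covers the whole study but the duration rule stops the clock at the last dose, so a rate responder can have a shortened period or none in the duration table

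*SAP*

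**What the plan says.** The text is in SAP 2.7.1.7, where the transfusion endpoint follows time to complete remission under the same heading. Protocol 12.5.1.8 carries the same duration rule.

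- **Rate.** A subject counts if transfusion-free "during at least 8 consecutive weeks after enrollment". Table 2-6 of the SAP agrees: "Post-baseline: subjects having received 0 units of transfusion within any 8 consecutive weeks during the course of the study". Neither is limited to time on treatment.
- **Who enters the duration summary.** Anyone with one or more such periods after baseline. What is reported for them: "the total duration of all transfusion independence periods (which all individually must be at least 8 weeks) will be also summarized".
- **Start of a period.** "The duration of each period of transfusion independence is defined from the end date of the last transfusion received".
- **End of a period.** The next transfusion, "or last date of treatment administration in case transfusions had not (re-)started during treatment". SAP 2.1.1.4 defines the last administration as the last non-zero dose of any component.
- **Data after treatment.** Protocol 6.2.1: "Transfusion should be collected every 2 months during post-treatment follow-up". SAP 1.1 lets subjects who stop treatment for reasons other than progression enter the extension phase, and sets safety follow-up of 150 days after the last MBG453 dose.

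No censoring rule is given for this duration.

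**The concern.** The duration summary reads as a description of the rate responders. The two derivations use different windows, so they need not describe the same people. Transfusion-free time after the last dose can make someone a responder, but it cannot contribute to that person's duration.

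Two consequences follow. The duration table can omit subjects whom the rate table counts, with nothing to show the reader that this has happened. And a period still running at the last dose is summed as if it had ended there, although no transfusion was given. The SAP handles ongoing duration of CR, PFS and LFS differently (2.7.1.6, 2.7.1.2, 2.7.1.4): it censors them.

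**Working it through.** The plan states no figure for this rule, so there is none to reproduce. The check applies both derivations to the same assumed transfusion histories.

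**Inputs from the documents**
- Cycle length is 28 days (SAP 1.1), so day d of cycle c is study day 28 × (c − 1) + d.
- Minimum period is 8 weeks = 8 × 7 = 56 days (SAP 2.7.1.7).
- Follow-up after the last MBG453 dose is 150 days (SAP 1.1). This exceeds 56, so the rate can be met entirely after the last dose.

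**Assumptions**
- The last dose is MBG453 on Day 8 of the final cycle.
- Transfusion status is known to 150 days after it.
- All transfusions are MDS-related.
- There is no HSCT or new anti-neoplastic therapy.
- The rate is read as zero units, as in Table 2-6.

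**Rules as written**
- Rate: responder if any 56 transfusion-free days fall between Day 1 and the end of follow-up.
- Duration: next transfusion minus last transfusion if the next one is on or before the last dose; otherwise last dose minus last transfusion. Keep only values of at least 56.

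**Case A, early stop.** Last dose C2D8 = 28 × 1 + 8 = Day 36. Last transfusion Day 10, none to Day 36 + 150 = 186.
- Observed: 186 − 10 = 176 days, so a responder.
- SAP period: 36 − 10 = 26 days, below 56. No qualifying period.

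**Case B, full core phase.** Last dose C13D8 = 28 × 12 + 8 = Day 344. Transfusions on Days 20 and 100, none to Day 344 + 150 = 494.
- Observed final period: 494 − 100 = 394 days.
- SAP final period: 344 − 100 = 244 days, so 150 days are cut and the period is shown as finished.
- With the earlier period of 100 − 20 = 80 days, the SAP total is 324 against 474.

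**Case C, transfused after the last dose.** Last dose C5D8 = 28 × 4 + 8 = Day 120. Transfusions on Days 20, 60, 95 and 130, none to Day 120 + 150 = 270.
- Observed: 270 − 130 = 140 days, so a responder.
- Periods before the last dose: 60 − 20 = 40, 95 − 60 = 35 and 120 − 95 = 25 days. None reaches 56.
- Last period by formula: 120 − 130 = −10 days. The 56-day minimum removes it when applied to this derived length. No qualifying period.

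| Case | In the rate? | Total by the SAP rule | Total if periods run to next transfusion or end of follow-up |
|---|---|---|---|
| A | Yes | none | 176 |
| B | Yes | 324 | 474 |
| C | Yes | none | 140 |

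If the rate were instead restricted to time up to the last dose, A and C would not be responders, and B would be one with a total of 324. Either choice makes the two outputs agree.

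**The case against.** **An on-treatment duration is a legitimate target.** The rule refers to restarting during treatment, and SAP 2.4.2 summarises transfusions before and on treatment. Ending at the last dose also avoids crediting study treatment with independence achieved after HSCT or next-line therapy, in line with SAP 2.7.3, which stops the CR determination at either event. This stands. A reader might infer that the reported duration is biased downward, but that presumes a whole-study target, which the documents do not establish. What remains is that the rate then uses a different window from the duration.

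**Negative durations.** A reader might also infer from Case C that negative values will appear in the table. The documents do not support that: the 8-week minimum drops a negative value if tested on the derived length. It would survive only if the minimum were tested on the observed interval and the last-dose rule applied afterwards. The SAP does not state the order, so this is a gap in specification.

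**The comparison with DOR, PFS and LFS is imperfect.** Those are single time-to-event endpoints, whereas this is a descriptive sum of periods. That is a fair reason not to replace it with a Kaplan-Meier analysis of the longest period, which would be a new endpoint. It does not justify presenting an ongoing period as complete.

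**The number affected may be small.** Becoming transfusion dependent is a progression criterion (Protocol Table 8-2), and progression is a reason to stop treatment (Protocol 9.1.1), so some who stop will not be transfusion-free. This also stands. Any simulated percentage would rest on assumed off-treatment follow-up and transfusion patterns that the documents do not give.

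**Timing.** The duration rule is protocol text, and the current SAP addendum is recorded as after database lock. This bears on how a change is documented. It does not remove the inconsistency.

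**Conclusion.** The inconsistency is in the current text of both documents. Followed literally, a rate responder with transfusion-free time after the last dose has a shortened period reported as complete (Case B) or no qualifying period (Cases A and C). The mechanism follows from the rules alone; the day counts rest on the assumed histories. How many of the 39 subjects are affected cannot be known from the documents, and no percentage is claimed.

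The consequence is limited. This is a descriptive summary of a secondary endpoint with no hypothesis test. It should still be corrected, because the rate and duration tables will be read together.

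**What to change.** Derive both outputs from one window, by one of two routes.

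1. **On-treatment.** Restrict the rate to the on-treatment window already used for the duration, and say so in the table titles.
2. **Whole study.** End each period at the next MDS-related transfusion. Otherwise end it at the earliest of the last date with known transfusion status, the start of new anti-neoplastic therapy or HSCT, and the data cut-off. Flag periods still ongoing at that date as censored.

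Under either route, apply the 8-week minimum to the same interval that is summed.

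No new data are needed, since Protocol 6.2.1 already collects transfusions after treatment. The cost is some reprogramming and a small departure from Protocol 12.5.1.8, which should be recorded in SAP section 4 as a change made after database lock.

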2.7.2 Statistical hypothesis, model, and method of analysis

No formal hypothesis testing is planned for this study.

2.7.3 Handling of missing values/censoring/discontinuations

Missing data for safety and efficacy endpoints will not be imputed.

For the determination of CR, only assessments post enrollment and prior start of any other anti-neoplastic therapy or HSCT are considered.

For the determination of PFS events, only assessments post enrollment and prior start of any other anti-neoplastic therapy are considered. If disease progression/relapse from CR or death is documented after two or more missing response assessments, PFS will be censored at the last adequate response assessment prior to the event.

For PFS and duration of CR, an adequate response assessment is considered any disease assessment indicating response status apart from “unknown” or “not done”.

A subject whose disease has not progressed or died by the date of the analysis cut-off will have their PFS censored at the time of the last adequate tumor evaluation performed on or before the cut-off date. Clinical deterioration will not be considered as documented disease progression.

Further details were already described in [Section 2.7.1](#).

